- Male patients, even if surgically sterilized (ie, status post-vasectomy), must agree to one of the following: practice effective barrier contraception during the entire study treatment period and through 90 days after the last dose of study drug, or must also adhere to the guidelines of any treatment-specific pregnancy prevention program, if applicable, or agree to practice true abstinence when this is in line with the preferred and usual lifestyle of the subject. (Periodic abstinence (eg, calendar, ovulation, symptothermal, post-ovulation methods] and withdrawal are not acceptable methods of contraception.)
- No evidence of uncontrolled bacterial, viral or fungal infections at the time of enrollment.
- No known active hepatitis B or C virus infection, or known human immunodeficiency virus (HIV) positive.

Exclusion Criteria:

- Patients with active \geq grade 3 peripheral neuropathy or grade 2 with pain on clinical examination during the screening period will be excluded.
- Patients with history of allergy and/or intolerance to MLN9708 are not eligible.
- Known GI disease or GI procedure that could interfere with the oral absorption or tolerance of MLN9708 including difficulty swallowing is not permitted.
- Patients receiving (or status post) a cord blood or a haplo-identical allograft will not be eligible.
- Patients undergoing (or status post) a T-cell depleted allogeneic transplantation will not be eligible.
- Patients receiving (or status post) conditioning regimens containing antithymocyte globulin, and/or campath, one receiving post-HCT planned cyclophosphamide will not be eligible.
- Method of stem-cell collection from the donor will be at the discretion of the treating physician. Although it is anticipated that majority of patients will receive allograft

mobilized with G-CSF alone; however donors receiving allografts mobilized with experimental agents (e.g. plerixafor) will remain eligible for the study.

- Patients experiencing disease relapse (for those in complete remission at the time of HCT) or progression (for those in partial remission, stable or refractory disease at the time of HCT) will be excluded.
- Donor lymphocyte infusions between day zero of HCT and first dose of MLN9708 are not permitted.
- Rituximab (or other B-cell depleting monoclonal antibodies) or bortezomib administration between day zero of HCT and before the first day of MLN9708 is not permitted.

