Table 2. Phase I dose escalation schema.

MLN 9708 Phase I dose Levels	Oral Dose (given on days 1, 8, 15 and 22)
-1	2.3 mg
1	3.0 mg
2	4.0 mg

- Dose escalation will start at dose level 1 and will be carried out according to standard 3+3 design. If 0 of 3 patients experiences DLT, dose escalation will proceed to the next higher dose level, at which 3 patients will be enrolled. On observing a DLT, the cohort will be expanded to 6 patients. Dose escalation will continue if no greater than 1 of 6 patients experience DLT, up to a maximum dose of 4mg. If 0 of 3 patients experiences DLT at dose level 2, then it will be considered MTD. If 2 or more patients experience a DLT, dose escalation will halt and the dose level below will be expanded to 6 patients to determine the MTD. If the dose level below already has 6 patients, enrolled, then it will be considered the MTD. If 2 or more patients experience DLT on first dose level (i.e.

dose level 1), then patients will be enrolled on dose level -1. No intrapatient dose escalation will be permitted.

- MTD is defined at maximum dose level with fewer than 2 of 6 patients experiencing DLT.
- Toxicity will be evaluated according to *CTCAE v4.0*. DLT will be defined as shown in Table 3. DLT observation period will be from first dose of MLN9708 to 28 days after the last dose. Dose escalation to higher dose level will require the last patient on the previous dose level to be out of DLT observation period.

Table 3. Definition of DLT for patients receiving MLN9708

Non-hematologic toxicities

- Grade 2 peripheral neuropathy with pain or Grade 3 or greater peripheral neuropathy, (definitely or probably) related to MLN9708
- Any grade 3-4 non-hematologic toxicity (definitely or probably) related to MLN9708, with the exception of alopecia, transient electrolyte or LFT abnormalities which resolve to \leq grade 1 within 72hours, Grade 3 arthralgia/myalgia, and brief (<1 week) Grade 3 fatigue
- Grade 3 or greater nausea and/or emesis (not due to GVHD) despite the use of optimal anti-emetic prophylaxis. Optimal anti-emetic prophylaxis is defined as an anti-emetic regimen that employs a 5-HT3 antagonist given in standard doses and according to standard schedules.
- Grade 3 or greater diarrhea (definitely or probably) related to MLN9708 that occurs despite maximal supportive therapy.

Hematologic and infectious toxicity

- Drop in donor myeloid-cell chimerism by more than 50% at day +90 (± 7 days) (in the absence of relapsed disease)

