- Tapering of any concomitant acute GVHD prophylaxis will be per institutional guidelines, however in absence of acute GVHD, renal insufficiency and disease relapse/progression it is recommended that taper **SHOULD NOT** commence before day +100. The recommended goal of tapering is the complete discontinuation of immunosuppressive medications by day +180.

Excluded Concomitant Medications and Procedures

The following medications and procedures are prohibited during the study:

Systemic treatment with any of the following metabolizing enzyme inhibitors is not permitted during this study. A DDI with a strong inhibitor would increase MLN2238 exposure.

- Concomitant administration of strong inhibitors of CYP1A2 (fluvoxamine, enoxacin, ciprofloxacin) and strong inhibitors of CYP3A (clarithromycin, telithromycin, itraconazole, voriconazole, ketoconazole, nefazodone, and posaconazole).

Systemic treatment with any of the following metabolizing enzyme inducers should be avoided unless there is no appropriate alternative medication for the patient to use. A DDI with a strong inducer would decrease MLN2238 exposure.

- Strong CYP3A inducers (rifampin, rifapentine, rifabutin, carbamazepine, phenytoin and phenobarbital).
- The dietary supplements St. John's wort and Ginkgo biloba are not permitted.
- Antibiotic prophylaxis will be given according to institutional guidelines. Herpes zoster prophylaxis per institutional guidelines will be required during prophylaxis with MLN9708.
- Patients missing a single dose of MLN9708 (due to decreased oral intake secondary to severe nausea, vomiting, mucositis etc.) should be discussed with study PI. Patients missing >1 dose will need to be replaced. In case MLN9708 therapy is interrupted, the time interval should be recorded.
- Toxicity will be evaluated according to CTCAE v4.0.
- Progression free survival (PFS) and overall survival (OS) following transplantation will be recorded.

Dose modification

- Patients experiencing a grade 3-4 hematological or non-hematological toxicity (as specified in CTCAE v4.0) thought to be related to MLN9708 will be removed from the study permanently (except the exceptions allowed in Table 3). No dose modifications are permitted.

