- If a patient experiences a Grade 3 or 4 non-drug-related renal function impairment or hepatic function impairment, MLN9708, can be held until recovery to Grade 1 or baseline (up to a maximum of 14 days). Upon recovery of the toxicity to a level allowing continuation of therapy, a dose reduction is not necessary.

Duration of therapy

MLN9708 will be continued until any one of the following criteria is met:

- Patient finishes four doses of MLN9708.
- Patient develops grade III-IV acute GVHD.
- Patient develops severe chronic GVHD.
- Patient develops any grade 3-4 toxicity related to MLN9708 use.

Data Safety Monitoring Plan

The Medical College of Wisconsin (MCW) Cancer Center (CC) Data Safety Monitoring Committee (DSMC) is responsible for monitoring data quality and subject safety for all cancer center investigator initiated clinical trials. A six to eight member Data and Safety Monitoring Committee will complete a review of protocol-specific data safety monitoring reports, to provide recommendations on trial continuation, suspension or termination.

A summary of the MCW CC DSMC activities are as follows:

- Review the clinical trial for data integrity and safety
- Review all unexpected grade 3, and all grade 4, and 5 adverse events, as well as any others requiring expedited reporting as defined in this protocol. (Grades 4 & 5 events must be reported to the DSMC within 5 calendar days of study staff's knowledge.)
- Review all DSMC reports
- Submit a summary of any recommendations related to study conduct
- Terminate the study if deemed unsafe for patients

A copy of the MCW CC Data and Safety Monitoring Plan and membership roster will be maintained in the study research file and updated as membership changes. The committee will

review reports from the study PI twice annually (or more frequently if needed) and provide recommendations on trial continuation, suspension or termination as necessary.

Any available DSMC letters will be submitted to the IRB of record as required.

6. Measurement of Effect:

Follow up schedule:

The schedule for follow up on the study is shown in the table below.

Study Visit	Approximate target Day Post-Transplant
1	60 days
2	67 days
3	74 days
4	81 days
5	90-100 days
6	180 days
7	365 days
8	2 years

Patients will be followed for survival, relapse and cause of death for 5 years post transplantation.

Phase I patients will be seen weekly for toxicity assessment during the DLT period.

GVHD Assessment:

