Unexpected also refers to adverse events or suspected adverse reactions that are mentioned in the investigator brochure as occurring with a class of drugs or as anticipated from the pharmacological properties of the drug, but are not specifically mentioned as occurring with the particular drug under investigation.

Adverse Event of Special Interest Definition: Adverse Events of Special Interest (AESIs) are a subset of AEs that are to be reported to Millennium on a quarterly basis by the sponsor-investigator. Millennium will provide the current list of AESIs and updates to the list will be distributed to the sponsor-investigator as appropriate.

Adverse Event Grading

Grade	Description
0	No AE (or within normal limits).
1	Mild ; asymptomatic or mild symptoms; clinical or diagnostic observations only; intervention not indicated.
2	Moderate ; minimal, local or noninvasive intervention (e.g., packing cauter) indicated; limiting age-appropriate instrumental activities of daily living (ADL).
3	Severe or medically significant but not immediately life-threatening; hospitalization or prolongation of hospitalization indicated; disabling; limiting self-care ADL.
4	Life-threatening consequences; urgent intervention indicated.
5	Death related to AE

Adverse Event Attribution

Relationship	Attribution	Description
Unrelated to investigational agent/intervention	Unrelated	The AE is clearly NOT related to the intervention
	Unlikely	The AE is doubtfully related to the intervention
Related to investigational agent/intervention	Possible	The AE may be related to the intervention
	Probable	The AE is likely related to the intervention
	Definite	The AE is clearly related to the intervention

Reporting of Adverse Events

AEs may be spontaneously reported by the patient and/or in response to an open question from study personnel or revealed by observation, physical examination, or other diagnostic procedures. Any clinically relevant deterioration in laboratory assessments or other clinical finding is considered an AE. When possible, signs and symptoms indicating a common underlying pathology should be noted as one comprehensive event. For serious AEs, the

investigator must determine both the intensity of the event and the relationship of the event to study drug administration.

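### No stop or hold is specified for MLN9708-related grade 2 painful neuropathy, although it is a DLT and a screening exclusion

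*Combined protocol and SAP*

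**What the plan says.** Four parts of the protocol bear on this event.

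- **Table 3 (Section 5)** counts as a DLT: "Grade 2 peripheral neuropathy with pain or Grade 3 or greater peripheral neuropathy, (definitely or probably) related to MLN9708".
- **Exclusion criteria (Section 3 and the Protocol Summary)** bar entry to patients with grade 3 or worse neuropathy, and likewise those with "grade 2 with pain on clinical examination during the screening period will be excluded".
- **Dose modification (Section 5)** says that patients with a grade 3-4 toxicity "thought to be related to MLN9708 will be removed from the study permanently", apart from the exceptions in Table 3. It adds: "No dose modifications are permitted". The only hold it describes is for grade 3 or 4 "non-drug-related renal function impairment or hepatic function impairment, MLN9708, can be held until recovery", for up to 14 days.
- **Duration of therapy (Section 5)** opens with "MLN9708 will be continued until any one of the following criteria is met". It then lists completion of four doses, grade III-IV acute GVHD, severe chronic GVHD, and "Patient develops any grade 3-4 toxicity related to MLN9708 use".

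The safety stopping table in Section 9 works at trial level and counts only related grade 3-4 events and graft rejection.

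**The concern.** The plan would not start MLN9708 in a patient who already has grade 2 neuropathy with pain, and for dose escalation it counts the same condition, when the drug causes it, as dose-limiting. Yet the rules for the individual patient say nothing about what to do when it appears between doses. The threshold for stopping sits at grade 3, one grade above the threshold at which the plan elsewhere treats the event as serious.

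The toxicity was foreseen. The introduction gives painful neuropathy as a drawback of bortezomib and a reason to study MLN9708 instead, and neuropathy on MLN9708 is a secondary objective. The drug is given as prophylaxis to patients without active chronic GVHD, so tolerance for continuing after such an event should be low. With a second site planned for phase II, the same event could also be handled in two ways.

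**Working it through.** **Applying the rules.** Take a patient with grade 2 neuropathy with pain, judged definitely or probably due to MLN9708, after dose 1.

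| Rule | Condition | Met? |
|---|---|---|
| Removal (Dose modification) | related, grade 3-4 | No, grade 2 |
| Dose reduction (Dose modification) | none allowed | Barred |
| Hold (Dose modification) | grade 3-4 renal or hepatic, not drug-related | No |
| Stop (Duration of therapy) | related, grade 3-4 | No, grade 2 |
| Trial-level boundary (Section 9) | related, grade 3-4 | Not counted |

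Nothing in the written rules is triggered. With doses on days 1, 8, 15 and 22, onset after dose 1, 2 or 3 leaves three, two or one dose. The reference to Table 3 in the removal rule only takes exceptions out of the grade 3-4 criterion; it does not add grade 2 with pain. No text says that a DLT ends that patient's own dosing. Table 3 serves the 3+3 escalation.

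**How many patients.** The plan gives no rate, so 1-5% is an assumption. The Protocol Summary gives 52 phase II patients (the stopping table in Section 9 uses 51, which makes no practical difference).

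- Expected number: 52 × 0.01 = 0.52; 52 × 0.05 = 2.6.
- Chance of at least one: 1 − 0.99^52 = 41%; 1 − 0.95^52 = 93%.
- Binomial 95th percentile: 2 at 1%, 5 at 5%.
- Chance of four or more: 0.2% at 1%, 26% at 5%.

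Only onset before dose 4 matters here, so the number affected by a stop rule is smaller. As context, the introduction reports grade 1/2 neuropathy of any kind in 6 of 52 patients in Study C16004 (6/52 = 11.5%), three of whom had grade 1 at entry. That study used weekly doses up to 3.95 mg/m². Here the maximum is four doses of 4 mg, which the protocol equates to about 2.23 mg/m². The upper end of 1-5% is therefore probably high. Six phase I patients without a DLT are too few to settle the rate.

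**Doses lost if a stop is added.** Planned doses are 52 × 4 = 208. If every event followed dose 1, the loss would be 0.52 × 3 = 1.56 doses (0.75%) at 1% and 2.6 × 3 = 7.8 doses (3.75%) at 5%. These are averages and upper limits on timing.

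**Replacements.** Section 5 replaces patients who miss more than one dose. Stopping after dose 1 or 2 meets that condition; stopping after dose 3 does not. On average this adds at most 0.52 to 2.6 patients, or up to 2.6 months at the slowest planned accrual of one per month.

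**Why the Section 9 boundary should stay as it is.** With looks at 12, 24, 36, 48 and 51 patients and limits of 3, 4, 6, 6 and 7, the exact probability of at least one hold is 5.8% at a true event rate of 5%. If grade 2 painful neuropathy were pooled in and raised the rate to 6%, it would be 10.3%; at 10%, 40.7%.

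**The case against.** The best reply is that the protocol is silent, not that it orders continuation. Doses are given under investigator supervision, and examination and toxicity assessment are scheduled on every dosing day. Section 5 foresees interruptions, since it asks that the interval be recorded. Patients may withdraw at any time. The Duration of therapy list is not exhaustive either: Section 11 requires permanent discontinuation for pregnancy, which the list omits. The background text names discontinuation as one way toxicities are managed and points to the Investigator's Brochure and Safety Management Attachment, which are not available here. All of this stands. A reader might infer that patients must be re-dosed, or that an investigator who stops breaches the protocol; the documents do not support that.

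A second reply is that Table 3 and the screening exclusion serve other purposes, and phase I is over with no DLTs. It is true that neither fixes a discontinuation threshold. They do show at what level the authors judged this toxicity important, and nothing explains why on-treatment patients should have a higher threshold.

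A third point concerns attribution. Section 11 places possible, probable and definite together under "Related to investigational agent/intervention", so one might extend the stop to possibly related events. That goes beyond Table 3, which requires definite or probable. Appendix B lists peripheral neuropathy among manifestations or complications related to chronic GVHD, so a merely possible link is weak ground for ending prophylaxis. A hold instead of a stop is a defensible alternative, but with only four weekly doses and no reductions allowed, a stop is simpler and matches the existing grade 3-4 rule.

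**Conclusion.** The gap is real and modest. The patient-level rules specify no stop or hold for related grade 2 neuropathy with pain and bar dose modification, while the plan elsewhere treats that event as dose-limiting and as a bar to entry. Followed to the letter, the list continues up to three further full doses unless someone exercises judgment. At an assumed 1-5%, 0.5 to 2.6 of 52 phase II patients would be expected to have the event, and fewer in time for a stop to matter. The textual finding does not depend on that range; its size does. The point does not touch the primary endpoint, the power calculation or the operating characteristics of the safety boundary. It should be corrected because the event is foreseeable and the correction is cheap, not because the trial is compromised without it.

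**What to change.** In Section 5, add one criterion to the Duration of therapy list: grade 2 painful peripheral neuropathy judged definitely or probably due to MLN9708, with a reference to Table 3. Add a sentence saying that this ends study drug only and that follow-up for GVHD, safety and survival continues. Do not put the item into the existing removal sentence, whose wording takes the patient off the study, unless that wording is changed to mean study drug. Leave the Section 9 grade 3-4 boundary unchanged.

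The cost is one list item and one sentence. No new assessments are needed, because toxicity is already checked at each dosing visit. Each affected patient loses one to three doses, and those stopped after dose 1 or 2 are replaced. Section 9 keeps replaced patients evaluable for safety but does not say that they stay in the efficacy count, so they appear to leave it. The same already happens to patients stopped for related grade 3-4 toxicity who miss more than one dose.

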A number of retrospective studies suggest protective role of statins against acute and chronic GVHD ¹⁷⁻¹⁹. Based on this data, our group conducted a single-arm phase-II study evaluating the safety and efficacy of atorvastatin for the prophylaxis of acute graft-versus-host disease in patients with hematological malignancies undergoing HLA-matched sibling donor hematopoietic SCT (www.clinicaltrials.gov NCT01175148). Atorvastatin administration in healthy donors and recipients was not associated with any grade 3-4 adverse events. The cumulative incidence rates of grade II-IV acute GVHD at days +100 and +180 were 3.3% (95%CI=0.2 - 14.8%) and 11.1% (95%CI=2.7-26.4%), respectively. The 1-year cumulative incidence of chronic GVHD was 52.3% (95%CI=27.6-72.1%). One-year cumulative incidences of non-relapse mortality and relapse were 9.8% (95%CI=1.4-28%) and 25.4% (95%CI=10.9-42.9%), respectively. The 1-year overall survival and progression-free survival were 74% (95%CI=58-96%) and 65% (95%CI=48-87%), respectively. Compared to baseline, atorvastatin administration in sibling donors was associated with a trend towards increased mean plasma interleukin-10 concentrations (5.6pg/ml vs. 7.1 pg/ml; p=0.06). This study showed that a novel two-pronged strategy of atorvastatin administration to both donors and recipients of matched sibling allogeneic HCT appears to be a feasible, safe and potentially effective strategy to prevent acute GVHD (*manuscript submitted for publication*). In an ongoing protocol, we are evaluating the role of atorvastatin for the prophylaxis of acute GVHD when administered to recipients of matched sibling and unrelated donor transplants alone, to assess if routine administration of atorvastatin to healthy sibling donors is warranted (www.clinicaltrials.gov NCT01665677). *The results of*

NCT01175148 and the preliminary observations from NCT01665677 suggest that while an atorvastatin-based GVHD prophylaxis provides protection against acute GVHD; compared to historical controls^{3, 4} the incidence of chronic GVHD remains high and represents a significant clinical challenge. This preliminary data underscores the need to develop prophylactic strategies for chronic GVHD in allogeneic transplant patients getting atorvastatin based acute GVHD prophylaxis in particular, and for patients undergoing allografting in general.

Role of B-cells in Pathogenesis of Chronic GVHD:

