- Unexplained immunologic graft rejection at day +90 (± 7 days) (define as donor myeloid-cell chimerism of <5%)
- Grade 4 neutropenia ($ANC <500/\text{mm}^3$) lasting ≥ 14 consecutive days, (definitely or probably) related to MLN9708
- Grade 3 neutropenia with fever and/or infection, where fever is defined as a temperature $\geq 38.5^\circ\text{C}$, (definitely or probably) related to MLN9708
- Grade 4 thrombocytopenia (platelets $<25,000/\text{mm}^3$) lasting at least 7 consecutive days, (definitely or probably) related to MLN9708

- The phase II portion will utilize the MTD for MLN9708, determined from phase I portion of the study. In phase II, patients will be enrolled in two independent cohorts of matched sibling and matched unrelated donor transplants.

- During the phase II portion, for chronic GVHD prophylaxis, four doses of MLN9708 will be administered orally on days 1, 8, 15 and 22, starting on day +60 to +90 post allogeneic HCT.
- All protocol-specific criteria for administration of study drug must be met and documented before drug administration. Study drug will be administered or dispensed only to eligible patients under the supervision of the investigator or identified sub-investigator(s). Patients should be monitored for toxicity, as necessary.
- Capsules of MLN9708 will also be referred to as study drug. Study drug will be supplied by Millennium as capsules of 2.3, 3.0 and 4.0 mg MLN9708.
- Patients should be instructed to swallow MLN9708 capsules whole, with water, and not to break, chew, or open the capsules. Study drug should be taken on an empty stomach (no food or drink) at least 1 hour before or 2 hours after a meal. Each capsule should be swallowed separately with a sip of water. A total of approximately 8 ounces (240 mL) of water should be taken with the capsules.
- All MLN9708 doses will be administered by authorized study personnel during patients' inpatient or outpatient visits, to ensure compliance. If the patient vomits after taking the study drug, the dose should not be repeated but should resume dosing at the time of the next scheduled dose. Missed doses can be taken as soon as the patient remembers if the next scheduled dose is 72 hours or more away. A double dose should not be taken to make up for a missed dose.
- Acute GVHD medications expected to be ongoing at the time of MLN9708 administration include calcineurine inhibitors (e.g. tacrolimus or cyclosporine) OR mycophenolate mofetil OR sirolimus OR atorvastatin.

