Chimerism will be evaluated using sorted whole blood in CD3 and CD33 fractions. For the purpose of this protocol, mixed chimerism is defined as the presence of donor cells, as a proportion of total cells to be < 95% but > 5% in the bone marrow or peripheral blood. Full donor chimerism is defined as ≥ 95% of donor cells. Mixed and full chimerism will be evidence of donor cell engraftment. Donor cells of ≤ 5% will be considered as graft rejection. Similarly, platelet recovery is defined as first day of platelet count $\geq 20,000 \times 10^9/L$, without transfusion for 7 consecutive days. Lineage specific chimerism analysis (myeloid, T-cell [B-cell if available] subsets), quantitative immunoglobulins and immune reconstitution will be performed at baseline (if not performed as standard of care at or around day +30) and then on approximately days +90, +180 and +365.

Secondary graft failure is defined as, ANC $<500 \times 10^9/L$ after post-transplant neutrophil recovery in the absence of disease relapse/progression. Immunological graft rejection is defined as detecting <5% donor myeloid cells on chimerism analysis.

7. Study Parameters (Study Calendar):

Patient Study Calendar:

The table below summarizes the patient clinical assessments over the course of the study.

Study Assessment	Screening ¹	MLN Dosing days (starting on day +60 to +90 post HCT)				Days Post Transplant (~±10 days up to day 365 and then ±28 days)						
		1	8±1	15±1	22±1	90-100	180	365	730	3 year	4 year	5 year
Informed consent	X											
H & PE ²	X	X	X	X	X	X	X	X	X	X	X	X
Vital signs ³	X	X	X	X	X	X	X	X	X	X	X	X
Karnofsky performance status	X	X	X	X	X	X	X	X	X	X	X	X
CBC/differential & platelet count	X	X	X	X	X	X	X	X	X			
Serum chemistries panel ⁴	X	X	X	X	X	X	X	X	X			
CMV quantitative PCR ¹²	X	X	X	X	X	X						
B-HCG serum pregnancy test ⁵	X											
Quantitative immunoglobulins ⁶	X					X	X	X	X			
Peripheral blood for chimerism	X ⁷					X	X	X				
Immune reconstitution panel ⁸	X					X	X	X	X			
CD34/CD3 cell dose infused	X											
Acute GVHD assessment	X	X	X	X	X	X	X	X	X			
Chronic GVHD assessment	X	X	X	X	X	X	X	X	X	X	X	X
Toxicity assessment ⁹	X	X	X	X	X	X	X	X	X			
Research specimens (optional) ¹⁰	X					X	X	X	X			
ANC and platelet recovery ¹¹	X											
Specify (if any) co-enrollment	X											

with other clinical trials											
----------------------------	--	--	--	--	--	--	--	--	--	--	--

Notes

H & PE= history and physical examination

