monitor and evaluate short term adverse events at each additional 12 patients who have been enrolled in the study. The expected 100 day post-transplant immunologic graft rejection (defined as less than 5% donor myeloid cells) rate is approximately 2.5% (in absence of relapsed disease) and the enrollment will be put on hold if more than 5% graft rejection rate is seen. For the development of grade 3-4 adverse events deemed to be related to MLN9708, the true rate is 5% and enrollment will be on hold if more than 10% adverse events are observed. The stopping boundaries for graft rejection and development of grade 3-4 adverse events are shown in Table below. In the case of a safety event suspending study, a prompt cumulative examination of all data and circumstances of these events will be conducted by the Medical College of Wisconsin DSMC to determine whether study should be resumed, whether the protocol will be revised or whether the study will be discontinued permanently.

Table. Stopping boundary for adverse events.

Number of patients enrolled	Stopping boundary for immunologic graft-rejection	Stopping boundary for developing grade 3-4 adverse events related to MLN9708
12	≥ 3	≥ 3
24	≥ 3	≥ 4
36	≥ 4	≥ 6
48	≥ 4	≥ 6
51	≥ 5	≥ 7

Accrual Estimate: 6-12 patients will be enrolled in the phase I part of the protocol. In the phase II portion a total of 52 patients (25 sibling and 27 unrelated donor transplantation) will be enrolled, with 1-3 per month. Total estimated accrual = 58 patients.

Accrual Period : Approximately 24-30 months

Follow-Up Period : Two years to evaluate incidence of acute and chronic GVHD and relapse pattern, and five years for survival outcomes.

10. Adverse Event Reporting Requirements

11. Definitions

The following are definitions of adverse events as defined by 21CFR312.32.

Types of Adverse Events

Adverse Event (AE) means any untoward medical occurrence associated with the use of a drug in humans, whether or not consider drug related. An AE can therefore be any unfavorable and unintended sign (including an abnormal laboratory finding), symptom, or disease temporally associated with the use of a medicinal (investigational) product whether or not it is related to the medicinal product. This includes any newly occurring event, or a previous condition that has increased in severity or frequency since the administration of study drug.

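### Section 6 defines immunologic graft rejection without excluding relapse, and gives a second, conflicting cut-off, so secondary objective 9 can count a relapse as a rejection

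*Combined protocol and SAP*

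**What the plan says.** Secondary objective 9 (Protocol Summary; repeated in Section 2) is the incidence of secondary immunologic graft rejection. Its operational definition is in Section 6, Chimerism Assessment and Immune Reconstitution: "Immunological graft rejection is defined as detecting <5% donor myeloid cells on chimerism analysis". Chimerism is measured at baseline and at about days +90, +180 and +365.

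The sentence before it defines secondary graft failure (objective 8) by a low neutrophil count "after post-transplant neutrophil recovery in the absence of disease relapse/progression". Earlier in the section, after mixed and full chimerism are defined, a further rule appears: "Donor cells of ≤ 5% will be considered as graft rejection". Mixed chimerism in that scheme is a proportion of total cells, in marrow or blood.

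Relapse is handled differently elsewhere:

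- Section 5, Table 3, chimerism-drop DLT: counted only "in the absence of relapsed disease".
- Section 5, Table 3, rejection DLT: "Unexplained immunologic graft rejection at day +90", with the gloss "define as donor myeloid-cell chimerism of <5" percent. Relapse is not named.
- Section 9, Safety/Stopping Rules: uses the same cut-off of less than 5% myeloid cells, and the expected 100-day "rate is approximately 2.5% (in absence of relapsed disease"). The hold trigger and the table heading do not repeat the qualifier.

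Section 9 names the outcomes to be analysed with competing events: acute and chronic GVHD, relapse and non-relapse mortality. Graft rejection is not among them.

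**The concern.** Loss of donor myeloid cells can mean that the host immune system has rejected the graft, or that the malignancy has returned and recipient cells have replaced donor cells. Only the first is immunologic rejection. A definition that rests on the chimerism value alone cannot separate the two, and this one is applied out to one year, while relapses accumulate.

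The omission looks like an oversight. Objectives 8 and 9 are a pair, their definitions stand in consecutive sentences, and no reason is given for treating relapse differently in them. At stake is what the reported rejection incidence means. A reader would take it as a possible harm of MLN9708, when part of it might be relapse, which objective 10 already reports.

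**Working it through.** The plan states no incidence, power or sample-size figure for objective 9, so there is nothing to reproduce. The check is to apply each rule, as written, to the kinds of patient who separate them.

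| Patient | Section 6 myeloid rule (<5%) | Section 6 total-cell rule (≤5%) | Other places |
|---|---|---|---|
| A: relapse, donor myeloid cells below 5% at day +180 or +365 | Rejection | Depends on total donor cells | Relapse under objective 10; not secondary graft failure; outside the population and window of the Section 9 expected rate |
| B: no relapse, donor myeloid cells below 5%, donor cells between 5% and 95% of total | Rejection | Mixed chimerism, which the section counts as engraftment | Below the Section 9 myeloid cut-off |
| C: no relapse, exactly 5% on whichever measure is used | Not rejection | Rejection | Not below the Section 9 cut-off |

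Patient A shows the missing exclusion: one biological event enters objectives 9 and 10, and no competing-event rule removes it. Patients B and C show that the two Section 6 rules disagree whether or not relapse is involved.

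**How far one case moves the rate.** Inputs: 52 phase II patients (Section 9, Accrual Estimate) and the 2.5% expected rate (Section 9, day 100, relapse excluded).

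- Expected rejections: 52 × 0.025 = 1.3. With the 51 patients of the stopping table, 51 × 0.025 = 1.3 as well.
- One misclassified case: 1/52 = 1.9 percentage points. Two: 2/52 = 3.8 points.
- With one true rejection, the reported proportion is 1/52 = 1.9%. One added case makes it 2/52 = 3.8%, and two make it 3/52 = 5.8%.

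**Section 9 boundaries, conditional illustration only.** The rejection boundaries are ≥3/12, ≥3/24, ≥4/36, ≥4/48 and ≥5/51. With X binomial (n, p) and p = 0.025, P(X ≥ boundary) at the five looks is 0.003, 0.021, 0.012, 0.032 and 0.009. Carrying the exact distribution forward from look to look, the chance of crossing at any look is 0.042. If relapse-related cases were also counted and raised the event rate to an assumed 5%, 7.5% or 10%, that chance would be 0.24, 0.52 or 0.74. The documents give no basis for choosing among these rates.

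**The case against.** Much of the case for a larger effect fails.

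**The stopping rule.** A reader might infer that safety monitoring is compromised. Section 9 does not rely on Section 6. It has its own myeloid definition, its own 100-day window and a relapse qualifier on its expected rate, and the natural reading is that the same event is counted. A crossing suspends enrolment and leads to DSMC review of the circumstances, where a relapse would be seen. What stands is that the qualifier is missing from the trigger and the table heading.

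**The benchmark.** A reader might infer that objective 9 will be judged against 2.5%. No passage says so. Objective 9 has no hypothesis, comparator or threshold.

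**Doubling or tripling.** It is tempting to take the sponsor's earlier sibling-donor study, "One-year cumulative incidences of non-relapse mortality and relapse were 9.8% (95%CI=1.4-28%) and 25.4% (95%CI=10.9-42.9%), respectively", and compute 52 × 0.254 = 13.2 relapses. If 10% of these fell below 5% donor myeloid cells, the rate would be (1.3 + 1.3)/52 = 5.0%; at 20%, (1.3 + 2.6)/52 = 7.6%. Over the relapse confidence interval, 0.025 + 0.10 × (0.109 to 0.429) gives 3.6% to 6.8%, and 0.20 in place of 0.10 gives 4.7% to 11.1%. These figures are not usable as estimates. They add a 100-day rate to a 1-year rate. They apply relapse from transplant to patients enrolled ideally at days +60 to +90, with those already relapsed or progressed excluded. They ignore the eligibility of bone marrow failure syndromes. They also rest on a 10% to 20% fraction that has no source.

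**The DLT contrast.** The rejection DLT excludes relapse only by implication, through its first word; the explicit exclusion belongs to the chimerism-drop item. Phase I is also finished, with no DLTs reported.

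**The lineage conflict.** One could argue that a low sorted CD3 result alone is rejection under the 5%-or-less rule. Because that scheme refers to total cells, this is not the obvious reading. The conflict between total and myeloid cells, and at exactly 5%, remains.

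Finally, relapse dates and sorted chimerism are collected, so cases could be separated at analysis. That is true, but the written definition does not call for it.

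**Conclusion.** The point holds for the endpoint definition. Followed literally, Section 6 classes relapse-driven loss of donor myeloid cells as immunologic rejection for secondary objective 9, and it contains two rejection rules that disagree. This is a stated rule that misclassifies, not merely missing detail.

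The size cannot be estimated from the documents. With about 1.3 rejections expected among 52 patients, one or two misclassified cases would change the reported rate materially, by 1.9 or 3.8 percentage points. That arithmetic uses the 100-day expected rate only to show how few events there may be, and does not predict the 1-year incidence.

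The direct effect is confined to a descriptive secondary endpoint. The safety rule is affected only if its events are counted without the relapse exclusion, which the text leaves possible but does not direct. The primary chronic GVHD analysis is untouched.

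**What to change.** - Use one endpoint definition for objective 9: fewer than 5% donor cells in the sorted myeloid (CD33) fraction, with no relapse or progression of the underlying disease. State how a chimerism fall that precedes documented relapse is classed.
- Delete the 5%-or-less sentence, or align it with this definition in cell population and cut-off.
- Add graft rejection to the competing-event paragraph of Section 9, with relapse as a competing event, so that no patient's relapse is also counted as a rejection.
- List patients with relapse-associated loss of donor myeloid cells separately.
- In Section 9, reconcile the hold trigger and the table heading with the relapse qualifier on the expected rate, so that the event counted is the event for which the rate is given.

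The cost is a wording amendment. Lineage-sorted chimerism and relapse follow-up are already in the plan, and no visit, test or sample-size change is needed.
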